8.1. Primary objective

• To assess the risk of neuroinflammatory/ophthalmic new onset of autoimmune disease(s) (NOAD) and other pre-specified NOAD within 12 months following the administration of the first dose of Cervarix:

[1] Neuroinflammatory/ophthalmic autoimmune diseases:

- Multiple Sclerosis
- Transverse myelitis
- Optic neuritis
- Guillain-Barré syndrome, including Miller Fisher syndrome and other variants
- Other demyelinating diseases:
 - Acute disseminated encephalomyelitis, including site specific variants: e.g. non-infectious encephalitis, encephalomyelitis, myelitis, myeloradiculomyelitis
 - AI peripheral neuropathies and plexopathies (including chronic inflammatory demyelinating polyneuropathy, multifocal motor neuropathy and polyneuropathies associated with monoclonalgammopathy).
- Auto-immune uveitis

[2] Other autoimmune diseases:

- Systemic lupus erythematous
- Autoimmune (AI) disease with rheumatologic conditions:
 - Rheumatoid arthritis (RA)
 - Juvenile rheumatoid arthritis (JRA)
 - Still's disease
 - Psoriatic arthritis
 - Ankylosing Spondylitis
- AI haematological conditions:
 - Idiopathic thrombocytopenic purpura (ITP)
 - AI haemolytic anaemia
- AI endocrine conditions:
 - Type 1 diabetes mellitus
 - AI thyroiditis including Hashimoto's disease, Graves' /Basedows' disease
- Inflammatory bowel / hepatic diseases:
 - Crohn's diseases
 - Ulcerative colitis
 - Autoimmune hepatitis

8.2. Secondary objectives

- To describe individually the incidence of the pre-specified NOAD considering different time periods following the administration of the first dose of Cervarix:
 - Incidence of Guillain Barré syndrome (including Miller Fisher syndrome and other variants), and autoimmune haemolytic anaemia within two months following the administration of the first dose of Cervarix;
 - Incidence of idiopathic thrombocytopenic purpura (ITP) within six months following the administration of the first dose of Cervarix;
 - Incidence of multiple sclerosis, transverse myelitis, optic neuritis, other demyelinating diseases ³, auto-immune uveitis, systemic lupus erythematous (SLE), rheumatoid arthritis (RA), juvenile rheumatoid arthritis (JRA), Still's disease, psoriatic arthritis, ankylosing spondylitis, type 1 diabetes mellitus, auto-immune thyroiditis (including Hashimoto's disease, Graves'/Basedows' disease), and inflammatory bowel / hepatic disease (Crohn's disease, ulcerative colitis and autoimmune hepatitis) within one year following the administration of the first dose of Cervarix.

Refer to Section 9.3 for the definition of the primary and secondary endpoints and the pre-specified list of NOAD.

8.3. Exploratory objective

• To evaluate if temporal clustering of the individual NOADs comprising the primary endpoint and the secondary endpoints (i.e., those NOADs on the pre-defined list) occurs following the administration of at least one dose of Cervarix® within the 12-month follow-up period.

9. **RESEARCH METHODS**

9.1. Study Design

9.1.1. Overview

- This is an observational cohort study using the CPRD GOLD data source in the UK.
- Four cohorts will be defined based on exposure to Cervarix and sex as recorded in the CPRD GOLD data source:

³ Other demyelinating diseases:

⁻ Acute disseminated encephalomyelitis, including site specific variants: e.g. non-infectious encephalitis, encephalomyelitis, myelitis, myeloradiculomyelitis

⁻ AI peripheral neuropathies and plexopathies (including chronic inflammatory demyelinating polyneuropathy, multifocal motor neuropathy and polyneuropathies associated with monoclonalgammopathy).

- 1. Cervarix vaccinated (exposed) female cohort
- 2. Unexposed historical female cohort
- 3. Unexposed concurrent male cohort
- 4. Unexposed historical male cohort
- Study population:
 - Female population is composed of female subjects vaccinated with Cervarix between the ages of 9 to 25 years and unexposed female subjects identified from historical data.
 - Male population is composed of 9- to 25-year-old male subjects not vaccinated with Cervarix.

Female subjects included in the exposed cohort will have received at least one dose of GSK's vaccine Cervarix administered according to local practice.

Female subjects in the unexposed historical cohort will be frequency matched for age and practice region identifier to the subjects included in the vaccinated (exposed) cohort.

Study design:

Comparison of the unexposed concurrent male cohort with the unexposed historical male cohort will be used as an internal control for changes over time in CPRD GOLD in reporting NOAD. The male subjects will be frequency matched for age and practice region identifier as described in Section 9.2.

A self-control case-series (SCCS) analysis for confirmed NOAD in the exposed female cohort will also be conducted, using a risk period of one year after the first Cervarix dose, a control period of one year and a six-month buffer period between risk and control periods.

9.1.2. Rationale for study design

NOAD represent a heterogeneous group of diseases with different clinical conditions and disease progression. Some NOAD present with a chronic disease pattern of relapse over time e.g. multiple sclerosis or systemic lupus erythematous, or an acute disease pattern (e.g. Guillain Barré Syndrome).

In addition to the comparison of the exposed vs. non-exposed cohort (cohort design), the confirmed NOAD in the exposed cohort will also be analysed using a self-control case-series (SCCS) analysis.

In the cohort design, specified NOAD will be collected over a period of one year following the administration of at least one dose of Cervarix in an exposed cohort and over a comparable period in the unexposed cohorts as shown in Figure 1. Four cohorts will be constituted as shown in Figure 1. The unexposed male cohorts will be enrolled in order to assess a possible change over time in the incidence rate of NOAD in CPRD GOLD independent of Cervarix introduction. The cohorts will be frequency

116239 (EPI-HPV-040 VS UK)

Protocol FDA - EMA PASS Final Version 1 matched for the age (age class of one year) and practice region identifier at reference date (age at first dose of Cervarix).

An unexposed concurrent female cohort has been not chosen as the unvaccinated group for the following reasons:

- There is a under-reporting of HPV vaccination in CPRD GOLD as evidenced by the difference in vaccine coverage in CPRD GOLD population and the UK population (see Table 2), an exposed concurrent cohort would include both true and false unexposed subjects;
- Moreover, because of the large vaccine coverage in the UK, non-vaccinated women could have different health care behaviour compared to the vaccinated women, resulting in a difference in the probability to detect auto-immune disease.

Therefore, the reference date (time = 0) for the vaccinated (exposed) cohort will be the date of the first dose of Cervarix recorded in CPRD GOLD. The reference date for the unexposed (unvaccinated) cohorts will be a date randomly selected among the reference dates of the exposed subjects and minus 3 years for the historical cohorts.

[figure not shown]
Figure 1 Cohort design

Note: all three doses may not have been administered

For the SCCS analysis, the exposed female cohort will be followed during a total period of 30 months from the first dose. The risk period will be defined as one year after the first dose, including the six months after the last dose when the full three-dose vaccination course is administered. A control period of the same duration will be defined, excluding the periods after subsequent doses. To control for a possible late effect of the vaccine, the control and the risks period will be separated by a six-month buffer period (Figure 2). For analysis of individual diseases, specific risk period could be defined.

light 2 Och control case series analysis	Figure 2	Self-control	case-series	analysis
--	----------	--------------	-------------	----------

Note: all three doses may not have been administered

The SCCS uses each subject as its own control, preventing virtually all potential confounding factors which do not vary with time (e.g. socio-economic status, gender, location) [Whitaker, 2006]. Additionally, fewer cases are usually required, as compared to a case-control design. The control period is chosen subsequent to the at-risk period. Age bias is not anticipated because the follow-up period is short compared to the age effect on incidence of autoimmune diseases (see Table 1).

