9.1.3. HPV vaccine coverage in UK and in CPRD GOLD

The submitted study is in the UK, which is a country with a high Cervarix vaccine coverage. The recommended schedule in the UK for HPV vaccination of 12-13 year old girls involves three doses of Cervarix given over at least a 6-month period [DH, 2008; HPA, 2010].

In the UK public HPV immunization program (12-13 year olds), HPV vaccination coverage in the UK for 2010/11 was 89.0%, 87.6% and 83.8% for the first, second and third dose respectively [Health Protection Agency, 2012].

Vaccination records in the CPRD GOLD cover only part of the Cervarix-vaccinated population in the UK. For instance, 70.7% of the 01-SEP-1996 – 31-AUG-1997 birth cohort were reported as HPV vaccinated in CPRD GOLD versus 85.9% reported by the UK Health Protection Agency. Corresponding numbers for the 01-SEP-1994 – 31-AUG-1995 birth cohort are 70.6% versus. 81.9% (Table 2).

Table 2 HPV vaccination coverage in CPRD GOLD versus HPA-DH UK data

	CPRD† UK‡			UK‡
Birth cohort	N vaccinated	N total	%	%
01 SEP 1996 and 31 AUG 1997	16028	22685	70.7%	85.9%
01 SEP 1994 and 31 AUG 1995	16343	23143	70.6%	81.9%

† Data extracted from CPRD GOLD version ffqprd_smart_2012Q3

‡ From Health Protection Agency Department of Health [Health Protection Agency, 2012]

A first exploration of the CPRD GOLD database identified 148,731 subjects vaccinated with Cervarix between 2007 and 2010. The number of vaccinated women in the relevant age-range included in the CPRD GOLD is provided in Table 3. The number of HPV-vaccinated females in the CPRD GOLD appears to be sufficient for studying adverse events which have a low incidence after vaccination with Cervarix.

Table 3 Number of HPV-vaccinated females in the relevant age range included in the CPRD GOLD

Age range [years]	Number of subjects
[9-10]	16
[11-15]	82326
[16-20]	65080
[21-25]	866

Created by GSK Biologicals', 2012

Date extracted from CPRD GOLD version ffgprd_smart_2012Q3

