9.2.1. The UK HPV National Immunization Programme

The submitted study is in the UK, which is a country with a high Cervarix vaccine coverage. The recommended schedule in the UK for routine HPV vaccination of all girls at 12 to 13 years of age is [DH, 2008; HPA, 2010]:

- Vaccination at this age starts with a first dose of 0.5ml of Cervarix HPV vaccine
- The second dose of 0.5ml follows one to two months after the first dose
- A third dose of 0.5ml follows at least six months after the first dose

The UK has had sufficient Cervarix vaccination coverage to, in theory, enable data acquisition. A public immunisation programme targeting girls between 12-13 years of age including a catch-up programme for young women up to 18 years was undertaken during the academic year 2008/09. A phased catch-up programme for females born 1 September 1991 to 31 August 1995 during the 2008/09 academic year was completed by the end of the 2009/10 academic year. The programme was delivered largely through secondary schools [Crawford, 2009; Sheridan, 2009; Sheridan, 2010]. In the UK public HPV immunization program (12-13 year olds), HPV vaccination coverage in the UK for 2010/11 was 89.0%, 87.6% and 83.8% for the first, second and third dose respectively [Health Protection Agency, 2012]. The recommended age range for the UK programme matches the age range required by the FDA (9-25 years of age) for the post-licensure safety study.

The study population will be composed of female and male subjects, 9 to 25 years of age, registered in the CPRD GOLD.

The exposed cohort will be composed of female subjects vaccinated with at least one dose of Cervarix, with or without other recommended vaccines.

The unexposed historical female cohort will consist of frequency age-matched and practice region-matched female subjects from the period before the introduction of Cervarix. The unexposed concurrent male cohort will consist of frequency age-matched and practice region-matched by one-year classes (15, 16, 17, etc.) male subjects from the

period after the introduction of Cervarix. The unexposed historical male cohort will consist of frequency age-matched and practice region-matched male subjects from the period before the introduction of Cervarix.

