9.2.5. Exclusion criteria

9.2.5.1. Exclusion criteria for all cohorts

- Subjects with a diagnostic code of any auto-immune disease during the year prior to the reference date.
- Subjects who received at least one dose of unspecified HPV vaccine or Gardasil at any time before the reference date.
- Subjects who have been included in the other cohort.

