9.3. Variables

9.3.1. Primary endpoint

• Occurrence of new onset of confirmed⁴ autoimmune disease during the period of one year following administration of the first dose of Cervarix (risk period) among an exposed cohort and during an equivalent time period in the unexposed cohorts for the following two co-primary composite endpoints:

[1] Neuroinflammatory/ophthalmic autoimmune diseases:

- Multiple Sclerosis
- Transverse myelitis
- Optic neuritis
- Guillain-Barré syndrome, including Miller Fisher syndrome and other variants
- Other demyelinating diseases:
 - Acute disseminated encephalomyelitis, including site specific variants: e.g. non-infectious encephalitis, encephalomyelitis, myelitis, myeloradiculomyelitis
 - AI peripheral neuropathies and plexopathies (including chronic inflammatory demyelinating polyneuropathy, multifocal motor neuropathy and polyneuropathies associated with monoclonalgammopathy).
- Auto-immune uveitis

[2] Other autoimmune diseases:

- Systemic lupus erythematous
 - Autoimmune (AI) disease with rheumatologic conditions:
 Rheumatoid arthritis (RA)

⁴ Auto-immune disease diagnosis ascertainment by an expert physician panel (Section 9.4.2).

- Juvenile rheumatoid arthritis (JRA)
- Still's disease
- Psoriatic arthritis
- Ankylosing Spondylitis
- AI haematological conditions:
 - Idiopathic thrombocytopenic purpura (ITP)
 - AI haemolytic anaemia
- AI endocrine conditions:
 - Type 1 diabetes mellitus
 - AI thyroiditis including Hashimoto's disease, Graves' /Basedows' disease
- Inflammatory bowel / hepatic diseases:
 - Crohn's diseases
 - Ulcerative colitis
 - Autoimmune hepatitis

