9.9. Limitations of the research methods

Limitations and recommendations for the research methods

As mentioned previously, Cervarix vaccination administration was done in the UK in the schools and administration of Cervarix is not reported for all subjects in CPRD. The vaccination record in the CPRD GOLD may not be complete; if for a certain subject no vaccination code for Cervarix is registered, vaccination status is uncertain. Due to the potential for under-reporting of HPV vaccination, an unexposed historical cohort (before introduction of Cervarix in the UK) was chosen instead of an unexposed concurrent cohort.

116239 (EPI-HPV-040 VS UK) Protocol FDA - EMA PASS Final Version 1

Although, diagnosis and/or coding of auto-immune diseases could change over time. Moreover, a link with HES was recently implemented in CPRD GOLD since 2009. The HES data coverage period is actually longer than 2009: currently April 1997 to March 2012. As such, historical controls will have the potential to have linked data in the same way as the more recent exposed group. In order to assess the possible impact of changes in auto-immune diseases diagnosis/coding in CPRD GOLD and HES over time, two male cohorts will also be enrolled: a cohort concurrent to the exposed female cohort and a historical cohort selected at the same time period as the unexposed historical female cohort. However, it is recognized that incidence of auto-immune diseases might vary according to sex as well as according to the age group. These two cohorts will be useful to study potential change over time in CPRD GOLD due to recent access to HES data that might increase the number of auto-immune diseases coded in the database.

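### Exposed time zero is the first recorded dose, which may not be the first dose given; the look-back would then remove early post-vaccination events, and the protocol text does not measure how often

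*Protocol*

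**What the plan says.** Section 9.1.2 fixes the exposed cohort's reference date: it "will be the date of the first dose of Cervarix recorded in CPRD GOLD". The primary endpoint in 9.3.1 instead counts new onset "during the period of one year following administration of the first dose of Cervarix (risk period"), and the 2-, 6- and 12-month secondary endpoints in 9.3.2 also start at administration of the first dose.

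On delivery, 9.2.1 says: "The programme was delivered largely through secondary schools". On recording, 9.9 says that "administration of Cervarix is not reported for all subjects in CPRD" and that "The vaccination record in the CPRD GOLD may not be complete". Section 9.1.3 gives the evidence: in the 1996/97 birth cohort 70.7% "were reported as HPV vaccinated in CPRD GOLD versus 85.9% reported by the UK Health Protection Agency"; the 1994/95 pair is 70.6% and 81.9%. The protocol uses this under-recording for one purpose, to reject a concurrent unexposed female cohort (9.1.2, 9.9).

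Section 9.2.5.1 excludes, from every cohort: "Subjects with a diagnostic code of any auto-immune disease during the year prior to the reference date". Section 9.2.4.1 requires full vaccination dates but states no check that the first record is dose 1.

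**The concern.** Recorded first dose and administered first dose coincide only if dose 1 is recorded whenever a later dose is. Where dose 1 was given at school and not entered but a later dose was, the reference date falls after the true first dose: by one to two months if the record is dose 2, by six months or more if it is dose 3 (schedule in 9.2.1).

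Events in that gap are then removed, not merely moved. A code in the gap normally lies in the year before the reference date, so the girl is excluded under 9.2.5.1. An onset in the gap that is coded later fails ascertainment under 9.4.2, which accepts only onset within one year after the reference date. Unexposed reference dates are random, so the look-back can remove post-vaccination events only from the exposed cohort.

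If there is an early risk, this lowers the exposed incidence, which is the unwelcome direction in a safety study. No planned analysis would reveal it: the per-dose sensitivity analysis (9.7.5.1), both SCCS versions (9.7.9.2) and the scan statistics (9.7.9.3) rest on the same recorded doses, and the male cohorts carry no vaccine dates.

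**Working it through.** **1. Reproduce Table 2.** 16028/22685 = 70.65% and 16343/23143 = 70.62%, matching the stated 70.7% and 70.6%.

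**2. Capture among vaccinated girls.** s = recorded coverage / national coverage: 70.65/85.9 = 0.823 and 70.62/81.9 = 0.862. So 17.7% and 13.8% of vaccinated girls have no record at all.

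**3. Range for the misdated share (assumption; the protocol gives no dose-level rate).**
- All-or-none recording per girl: 0%.
- Each of three doses missed independently with probability m: any record has probability 1 − m³. Among recorded girls the first record is dose 2 with share m(1−m)/(1−m³) and dose 3 with share m²(1−m)/(1−m³).
  - m = 0.1: 9.9% misdated in total. m = 0.3: 28%.
  - m set so that 1 − m³ = s: for 1996/97, m = 0.562, giving 29.9% at dose 2 and 16.8% at dose 3, total 46.7%. For 1994/95, m = 0.516, giving 29.0% and 15.0%, total 43.9%.

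**4. Window lost per misdated girl.** First record dose 2: 1-2 of 12 months (8-17%), 50-100% of the 2-month window, 17-33% of the 6-month window. First record dose 3: at least half of the 12 months, and all of the 2- and 6-month windows.

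**5. Effect on the rate ratio.** Assumptions: background rate constant; excess risk follows dose 1 only and lasts k months; gap g = 1.5 months for dose 2 and 6 months for dose 3. For an analysed window of W months (k ≤ W), a girl's rate ratio is 1 + (RR−1) × max(0, k−g)/W, averaged over the shares. Shares used: 6% and 4% (10% misdated) and 30% and 16.8% (about 47%). RR = 2 while the excess lasts.

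| Excess lasts | Window | True | 10% misdated | 47% misdated |
|---|---|---|---|---|
| 12 months | 12 months | 2.00 | 2 − 0.06×0.125 − 0.04×0.5 = 1.97 | 2 − 0.30×0.125 − 0.168×0.5 = 1.88 |
| 2 months | 12 months | 1.17 | 1.15 | 1.10 |
| 6 months | 6 months (ITP) | 2.00 | 2 − 0.06×0.25 − 0.04 = 1.95 | 2 − 0.30×0.25 − 0.168 = 1.76 |
| 2 months | 2 months (GBS, haemolytic anaemia) | 2.00 | 2 − 0.06×0.75 − 0.04 = 1.92 | 2 − 0.30×0.75 − 0.168 = 1.61 |

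With RR = 1 every cell is 1. The same arithmetic applies to the SCCS if its control period is free of excess risk.

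**6. Power.** A pooled z calculation at 50,000 per cohort gives detectable RRs of 18.5, 3.72, 1.96 and 1.64 at 1, 10, 50 and 100 per 100,000, close to the stated 18.7, 3.7, 2.0 and 1.6 (9.5.1). At 50 per 100,000 and a sustained RR of 2.0, power is 82% with no misdating, 81% at 10% and 74% at 47%.

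**The case against.** **The evidence is at subject level.** Table 2 counts girls with any HPV record, and 9.9 speaks of subjects with no Cervarix code. Girls with no record never enter the exposed cohort and misdate nobody. A reader might infer that dose 1 is in fact missing for a known share of exposed girls. The documents do not show that; they say only that the record may be incomplete, and 0% is compatible with them. This stands in full.

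**A check may exist elsewhere.** Section 9.2.2 refers to Annex 5 for the stepwise identification of the exposed cohort, and the content of that annex is not in the text at hand. This stands: the absence of a check can be asserted only for the protocol body.

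**Some misdated girls are already removed.** Section 9.2.5.1 excludes anyone with an unspecified HPV vaccine or Gardasil record before the reference date, so a dose 1 entered under a non-brand code leads to exclusion. This stands for that route but does nothing for a dose 1 never entered.

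**The bias might be read as large and certain.** One could argue that at 47% misdated a true RR of 2.0 falls to 1 + (1 − 0.47) = 1.53. That requires every excess case of every misdated girl to fall in the gap. For girls first recorded at dose 2 (0.30/0.468, about two thirds of the misdated), the whole 12-month excess would have to fit into 1-2 months, a rate ratio in the gap of 1 + 12/2 = 7 to 1 + 12/1 = 13. Nothing in the documents supports this, and any risk from doses 2 or 3 themselves would reduce the attenuation further. Nor does the look-back lower the ratio regardless of the truth: with no vaccine effect it stays at 1.

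**The endpoints hit hardest are not confirmatory.** Section 9.7.6 says so of the individual-disease analyses. That limits the consequence, but these are where an early signal would be sought.

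**Conclusion.** The point holds as a possibility that the protocol creates and does not measure. The time origin differs between 9.1.2 and 9.3.1-9.3.2, the protocol gives reason to doubt that the two coincide, and the look-back turns any mismatch into a loss of early post-vaccination events in the exposed cohort.

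The misdated share is unknown, from 0% to about 44-47%; the upper end needs independent loss of more than half of all single doses. Given a real early effect, the co-primary 12-month composites are attenuated only slightly (2.00 to 1.97-1.88 for sustained risk). The 2-month endpoints could be attenuated markedly (2.00 to 1.92-1.61) and ITP at 6 months moderately (2.00 to 1.95-1.76). These figures assume that excess risk follows dose 1 only, with dose 2 at 1.5 months and dose 3 at 6 months.

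**What to change.** - **Exposed pool (9.2.2, 9.2.4.1).** Before drawing the 65,000, exclude any girl whose reference record is coded as a second or third dose. This uses only information available at the reference date, so it adds no immortal time. If Annex 5 already contains such a step, state it in the body.
- **Sensitivity analysis (cohort and SCCS).** Restrict to girls whose recorded sequence is compatible with a true dose 1, for example first two recorded doses one to two months apart. Label it sensitivity only: it conditions on a later dose, so it can drop girls who fell ill after dose 1, and it cannot classify girls with one record. A rule that treats any gap of two to six months as doses 2 and 3 would not serve. Under 9.2.1 those doses are normally at least four months apart (6 − 2), so a two-to-four-month gap more naturally suggests a late second dose after a correctly recorded first.
- **Reporting.** Tabulate recorded dose number and inter-dose intervals. Report look-back exclusions by month for the six months before the reference date, by cohort; an excess confined to the exposed cohort would be the warning sign.

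Cost: one selection rule, one sensitivity analysis and two tables. The exposed pool shrinks somewhat. Table 3 totals 16 + 82,326 + 65,080 + 866 = 148,288, but that is before the criteria in 9.2.4.1 and 9.2.5.1, so the eligible number should be confirmed. The first step also depends on whether the codes carry dose number, which the protocol text does not confirm; the interval tabulation needs only the dose dates.
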